### Demographic data

Several individual markers of treatment response will also be explored in the study.

The following areas will be assessed through direct questioning of the study participants:

- Age, sex and educational status.
- Duration of untreated depression.
- Age at first depressive episode.
- Psychiatric comorbidities (i.e. anxiety disorders, PTSD, OCD and personality disorders).
- Familial disposition for psychiatric disorders among first-degree relatives.
- Physical comorbidities (i.e. pain, cardiovascular disorders, diabetes and neurological disorders).
- Treatment history of depression.
- DART score at baseline.

Furthermore, individual characteristics of the participants will be examined. Specific patient traits could potentially guide future treatment decisions leading to enhanced treatment

outcomes, minimised side effects, and hopefully a reduction in the trial-and-error process, which is associated with finding the right treatment.

To explore the clinical utility of these individual characteristics, we aim to analyse how they are associated with treatment outcome in the context of the RCT, i.e. all three arms of the study.

## Patient Population

### Study population

Participants will include patients from general practice diagnosed with unipolar depressive disorder by a general practitioner, in which there is clinical uncertainty as to which of the initial treatments (medication or psychotherapy) would be most beneficial. Patients will be aged 18 to 65 at baseline.

Participants will be recruited from multiple general practices in the North Denmark Region by their general practitioner. 171 participants will be included with an expected dropout rate of 20%.

Symptomatic remission (i.e. remitters) is evaluated using the Hamilton Rating Scale for Depression, 6 item version (HAM-D6) and is defined as a score  $\leq 5$  (20). Symptomatic response (i.e. responders) is also evaluated using the HAM-D6 and is defined as a 50% reduction in the HAM-D6 score. For further details, see figure 2.

### Inclusion criteria

1. The participant must be referred to the study with a diagnosis of unipolar depressive disorder, as judge by the GP.
2. Severity of the depressive episode corresponding to moderate depression, as judged by the GP.
3. Clinical uncertainty regarding which of the treatments, medication or psychotherapy, would be the better choice in the case concerned.
4. Age criteria: Participants must be at least 18 years old and no more than 65 years old at the time of randomisation.

5. The participant must be a patient in general practice.
6. Participants must be able to participate in virtual meetings (e.g. by phone or computer) and have e-Boks.
7. The participant must be willing to receive psychotherapy by a psychologist and/or medication.
8. Must have signed the document of informed consent.

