## Aim of the study

The purpose of this study is to investigate the effectiveness of three different treatment pathways for moderate depressive episodes as part of unipolar depressive disorder, through a three-armed, open-label randomised controlled study. Participants will be allocated to one of the three groups in a 1:1:1 ratio.

The three treatment pathways will be as following:

1. Treatment as usual by a general practitioner (TAU-GP).
2. Treatment as usual by a psychologist (TAU-P).
3. An algorithm-based pharmacological treatment by a general practitioner (ALGO).

The primary outcome of the study is to examine whether there is a difference between the three groups. It will be measured by using a F-test from baseline to end of study at 12 weeks, using the Hamilton Depression Scale, 6 item version (HAM-D6).

Additionally, several secondary outcomes will be explored, e.g. the difference in differences (DID) between TAU-GP vs. ALGO, TAU-GP vs. TAU-P and TAU-P vs. ALGO.

The hypothesis is that a tailored algorithm-based treatment regarding patients with depression, treated in general practice, is more effective than treatment as usual (TAU), whether provided by general practitioners (GPs) or psychologists.

Furthermore, a qualitative study will be conducted to investigate the impact of the assigned treatment pathway from the participant's perspectives.

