## Methods and Material

### Study design

To address the aim of the study, an open-label, randomised controlled trial (RCT) will be conducted, as well as a qualitative interview.

Participants will be allocated in a 1:1:1 ratio to either: treatment as usual by a general practitioner (TAU-GP), treatment as usual by a psychologist (TAU-P) in the form of cognitive

behavioural therapy (CBT), or an algorithm-based medical treatment by a general practitioner (ALGO). The duration of the study is up to 14 weeks, with 12 weeks of treatment and up to 2 weeks between screening and baseline. Participants will be evaluated at baseline, 4 weeks, 8 weeks and 12 weeks after baseline, respectively. For all 3 arms, an external rater will carry out the Hamilton Depression Rating Scale (HAM-D) screening.

The study design and duration are illustrated in Figure 1.

[figure not shown]

Figure 1: Study Design (GP: General practitioner. TAU: Treatment as usual. PSE: Present State Examination).

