### Study intervention

In the two treatment as usual arms (TAU-GP and TAU-P), the choice of treatment and the frequency of patient consultations are at the discretion of the general practitioner (GP) and the psychologist. However, the psychologist will utilize cognitive behavioural therapy (CBT) as part of the treatment approach.

In the TAU-GP arm, the GP's can refer patients for psychotherapy, if deemed necessary, after initiation of medication. In the TAU-P arm, the psychologist may request initiation of medication through the general practitioner after psychotherapy, in the form of cognitive behavioural therapy (CBT), has been initiated.

For the algorithm-based treatment arm (ALGO), the GP drafts an individual, algorithm-guided stepped-care plan that merges measurement-based care with pre-set critical decision points (see figure 2). Every 2–4 weeks, validated symptom scores and side-effects are reviewed against evidence-based thresholds. Symptom scale score results are conveyed as “if-then” rules, triggering the next action, e.g. dose optimisation, switch, augmentation, or psychologist referral, as defined at baseline. These structured checkpoints prevent therapeutic drift and ensure the treatment keeps advancing until meaningful improvement is achieved, while still leaving room for clinical judgement and patient preference. The plan is based on the patient’s symptoms, previous treatment history, current clinical guidelines, possible side effects to antidepressants and the general practitioner’s clinical assessment.

The choice of treatment will follow predetermined steps, and the algorithm will include critical decision points (CDPs) at weeks 4, 8 and 12, where treatment efficacy is assessed. This assessment will lead to specific and predetermined adjustments regarding the current treatment (e.g. to continue current treatment or to change choice of treatment from the predefined plan) and in relation to preset “if-then” rules.

[figure not shown]
As a result of lack of tolerability to the current treatment, an earlier switch to an alternative treatment will be possible. In such cases, the algorithm will continue from that point, with a new HAM-D6 measurement conducted four weeks later.

Figure 2 illustrates the baseline measurement of HAM-D6, followed by initial treatment, and subsequent HAM-D6 measurements and treatment decisions at weeks 4 and 8.

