#### [Exclusion criteria](#)

1. Misuse of substances that might influence the study, as judged by the investigator.
2. Difficulty in understanding the Danish language, as judged by the investigator.
3. A diagnosis of dementia.
4. Medical conditions that might interfere with the study outcome or safety, judged so by the investigator.
5. Pregnancy.
6. High risk of non-adherence at the investigator's discretion.
7. Suicidality: according to C-SSRS with a positive response to question 4 or 5 within the last three months or upon investigator's discretion.
8. No current medical or psychotherapy treatment initiated within the last 4 weeks prior to screening.

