#### [Discontinuation criteria](#)

- Suicidality according to C-SSRS with a positive score to question 4 or 5 or upon the investigator's discretion.
- Severe somatic illness, as judged by the investigator.
- The patient wishes to stop participation and/or withdraws consent.
- The patient is unable to follow the treatment in one of the arms.
- Treatment will be terminated if the subject does not show up for two virtual meetings with the study staff or two meetings with the GP/psychologist, without cancelling, and

the study personnel are unable to get in contact with the participant. Attempts of contact are documented in the CRF.

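### Inclusion criterion 7, read literally, admits patients who will accept only medication or only psychotherapy, so the protocol allows loss after randomisation that depends on the allocated arm

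*Protocol*

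**What the plan says.** **Eligibility (Protocol, Inclusion criteria and Exclusion criteria).** Item 7 reads "The participant must be willing to receive psychotherapy by a psychologist and/or medication". Two other items come close to the question. Inclusion item 3 asks for "Clinical uncertainty regarding which of the treatments, medication or psychotherapy, would be the better choice in the case concerned". Exclusion item 6 is "High risk of non-adherence at the investigator's discretion".

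**Allocation (Aim of the study; Study design; Table of Measurements).** "Participants will be allocated to one of the three groups in a 1:1:1 ratio", and "an open-label, randomised controlled trial (RCT) will be conducted". Randomisation takes place at the screening visit. Baseline follows within 14 days, and the first HAM-D6 rating is at baseline.

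**Treatments (Aim of the study; Study intervention).** ALGO is named as a pharmacological pathway. In TAU-GP the GP "can refer patients for psychotherapy, if deemed necessary, after initiation of medication". In TAU-P medication may be requested once CBT has begun. In both usual-care arms the choice of treatment is otherwise left to the GP or psychologist.

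**Leaving the study (Discontinuation criteria; Withdrawal and dropout).** One discontinuation criterion is "The patient is unable to follow the treatment in one of the arms"; another is the patient's wish to stop. Meeting any criterion means withdrawal, without replacement. Outcome data are to be collected around the time of withdrawal if possible, with HAM-D6 first in priority.

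**Analysis set.** The primary analysis uses randomised patients with a HAM-D6 rating after baseline, with LOCF for those who stop early.

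**The concern.** The trial compares pathways that begin with different treatments. That comparison is protected only if every entrant would start whichever treatment is drawn. As worded, item 7 does not secure this: it is met by someone who will take tablets but not see a psychologist, and by someone who will do the reverse.

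Allocation is open, so such a patient learns the arm and can decline it. Whether they decline depends on the arm drawn. Psychotherapy-only patients would be lost mainly from ALGO, and possibly from TAU-GP. Medication-only patients would be lost from TAU-P. Even if the numbers lost are equal, the kinds of patients lost are not, and a larger sample does not repair that.

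**Working it through.** **1. Who meets item 7, and what they can start**

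| Entrant accepts | Meets item 7 | ALGO | TAU-GP | TAU-P |
|---|---|---|---|---|
| Both | Yes | Can start | Can start | Can start |
| Medication only | Yes | Can start | Can start | Cannot start as described |
| Psychotherapy only | Yes | Cannot start as described | Unclear: referral follows medication, but choice is the GP's | Can start |

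Inclusion item 3 concerns which treatment is clinically better, not what the patient will accept. Exclusion item 6 could catch a declared refuser, but only at discretion, and it does not mention refusal of one treatment.

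**2. What happens to a refuser**

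- A refuser who leaves between screening and baseline has no HAM-D6 at all and is outside the mITT set.
- A refuser who leaves after baseline and is rated promptly stays in the mITT set. LOCF then carries forward a rating taken largely without the assigned treatment.
- A refuser who leaves after baseline and is not rated again is outside the mITT set.

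**3. The plan's own sample size**

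Inputs (Power calculation): difference 2.25, SD 3.9, alpha 0.05, power 0.80, 45 per group, dropout 20%.

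- Take one arm differing from two equal arms: means 0, 0, 2.25, grand mean 0.75.
- Sum of squared deviations: 0.75² + 0.75² + 1.5² = 3.375.
- Noncentrality: 45 × 3.375 / 3.9² = 9.99. The F-test on 2 and 132 degrees of freedom has power 0.805, so 45 per group reproduces.
- 45 / 0.8 = 56.25, rounded up to 57; 57 × 3 = 171.

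These figures are not in dispute.

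**4. Patients allocated to a treatment they would not start**

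The shares are assumed; the protocol gives none. Expected number = patients in the arm(s) × share.

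| Assumed share | Psychotherapy-only, in ALGO (57) | Psychotherapy-only, in ALGO and TAU-GP if both are strictly medication-first (114) | Medication-only, in TAU-P (57) |
|---|---|---|---|
| 5% | 2.9 | 5.7 | 2.9 |
| 10% | 5.7 | 11.4 | 5.7 |
| 20% | 11.4 | 22.8 | 11.4 |

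**5. Effect on power**

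Let q be the total share accepting only one treatment, split between the two kinds from 25:75 to 75:25. Assume that every refusal is lost on top of the 20% dropout and that both GP arms are strictly medication-first. Evaluable patients per arm = 57 × 0.8 × (1 − share refusing that arm).

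Example, q = 20% with three quarters medication-only:

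- TAU-P: 57 × 0.8 × 0.85 = 38.8.
- Each GP arm: 57 × 0.8 × 0.95 = 43.3.
- F-test power: 0.76 if TAU-P is the differing arm, 0.78 if ALGO is.

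| q | Refusers in total | F-test power |
|---|---|---|
| 5% | 4–5 | 0.80 |
| 10% | 7–10 | 0.78–0.80 |
| 20% | 14–20 | 0.75–0.78 |
| 30% | 21–30 | 0.71–0.76 |

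**6. Effect on the contrast if refusers stay in through LOCF**

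Assume that refusers are carried forward with no change while others improve by 4 to 8 points. The shift in TAU-P against the GP arms is the improvement × the difference in refusal shares. At q = 20% split 75:25 this is (0.15 − 0.05) × 4 to 8 = 0.4 to 0.8 points, against a target of 2.25. At q = 10% it is 0.2 to 0.4. The sign reverses with the split, and at 50:50 this shift is zero.

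**The case against.** The wording has an innocent reading. Usual care may add psychotherapy to medication or medication to CBT, and ALGO can lead to psychologist referral, so a participant may receive one treatment or both. The criterion may have been meant to cover that. The point stands as an explanation of intent, but the text does not say so, and a site applying it literally enrols a single-treatment patient.

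There are also filters. The GP refers willing patients, the design and treatment options are discussed in person, consent is signed, and exclusion item 6 is available. These will remove some firm refusers. None of them is a rule that every arm must be acceptable.

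A reader might infer that a psychotherapy-only entrant has a 2/3 chance of an arm they refuse, with all 114 GP-arm patients exposed. The protocol does not support that as more than an upper bound. TAU-GP treatment is at the GP's discretion, and the sentence on referral does not clearly oblige the GP to prescribe to an unwilling patient. ALGO too leaves some room for patient preference, so its figures also rest on reading it as pharmacological from the start.

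A reader might also infer that refusers necessarily vanish from the primary analysis. They do not: the planned rating after withdrawal keeps some in the mITT set. That rating is conditional, however, and cannot serve as a post-baseline rating for someone who left before baseline.

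**Conclusion.** The concern holds as a defect of wording with a real but unquantified consequence. Criterion 7, read literally, together with open allocation at screening, the withdrawal rules and the mITT/LOCF definition, permits loss that depends on the allocated arm and on patient preference.

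On the assumed shares of 5% / 10% / 20%, about 3 / 6 / 11 psychotherapy-only patients in ALGO are affected, with 6 / 11 / 23 across both GP arms as the upper bound. The same shares of medication-only patients give about 3 / 6 / 11 in TAU-P. Under the assumptions shown, power stays at 0.78 or above when no more than 10% accept only one treatment, so the case rests on selective loss and not on power.

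Two stronger conclusions are not supported. The protocol does not show that the arms will cease to be comparable, because the number of single-treatment entrants is unknown and may be small. Nor does it show that refusals would use up the dropout allowance of about 11 per arm (20% of 57): that match arises only at an assumed 20% share, and the protocol does not say whether the 20% already includes refusals. The change is advisable; it does not call the design into question.

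**What to change.** Reword inclusion criterion 7 along these lines:

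*The participant must be willing to accept allocation to any of the three treatment arms, that is, willing to start medication if so allocated and willing to start psychotherapy by a psychologist if so allocated.*

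Naming each start separately matters. A phrase offering either one treatment or the other would keep the present ambiguity.

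The discontinuation criterion on inability to follow treatment does not say which arm is meant. The sponsor should reconcile that phrase with the amended criterion; no new discontinuation rule is proposed here.

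The cost is a one-line amendment. A few patients with a fixed refusal would not be enrolled. The sample size stays at 57 per arm and 171 in total.

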#### [Exclusion criteria](#)

1. Misuse of substances that might influence the study, as judged by the investigator.
2. Difficulty in understanding the Danish language, as judged by the investigator.
3. A diagnosis of dementia.
4. Medical conditions that might interfere with the study outcome or safety, judged so by the investigator.
5. Pregnancy.
6. High risk of non-adherence at the investigator's discretion.
7. Suicidality: according to C-SSRS with a positive response to question 4 or 5 within the last three months or upon investigator's discretion.
8. No current medical or psychotherapy treatment initiated within the last 4 weeks prior to screening.

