## Flowchart of Participant's Course

## Table of Measurements

Week	-2 to -1 Screening	0 Baseline	4	8	12 End of Study	Un-scheduled visit
Meeting form	In person	Virtual meeting	Virtual meeting	Virtual meeting	Virtual meeting	Virtual meeting
Signed Consent Form	X					
Inclusion and exclusion criteria	X					
Oral + written information	X					
Randomisation	X					
Adverse events		X	X	X	X	X
Demographic data	X					
Rating Scales						
HAM-D6		X	X	X	X	X
C-SSRS	X	X	X	X	X	X
PSP		X	X	X	X	
DART		X				
PSE						X*
Self-report forms						
MDI		X	X	X	X	
Brief INSPIRE-O		X	X	X	X	

HAM-D6: The Hamilton Depression Scale, item 6.

C-SSRS: The Columbia-Suicide Severity Rating Scale.

PSE: Present State Examination.

MDI: Major Depression Inventory.

PSP: The Personal and Social Performance Scale.

DART: The Danish Adult Reading Test.

\*In person

All visits and phone calls are scheduled within the defined time frame +/- 3 days. Pre-screening is conducted by a phone call by the investigator or study staff. The written study information will be sent in advance of the screening visit, and if the patient prefers, the letter of consent will also be sent prior to screening. The screening visit is a physical meeting where oral and written information is presented, and written consent can be obtained. Should the patient wish to, they can have at least 24 hours and no more than a week to consider the consent form. A follow-up meeting will be scheduled.

If, during the screening visit, the patient is found to meet all criteria for trial participation, the first treatment visit (baseline visit) will be scheduled within 14 days of the screening. The patient is randomised to treatment at screening.

A virtual baseline meeting is scheduled with the investigator or a competent research assistant. Study visits (virtual meetings) at 4, 8 and 12 weeks, as well as potential telephone calls, are scheduled with the investigator or study staff. Both screening and baseline visits are study related.

Table 1 further visualises the duration of time of each rating scale and interview as well as type of the rating scale, along with the duration of time and type for the different kinds of visits.

	Duration	Type
C-SSRS	1. visit 20 minutes (hereafter 5 minutes)	Rating scale - Interview
PSP	15 minutes	Rating scale - Interview
DART	5 minutes	Rating scale - Interview
HAM-D6	15 minutes	Rating scale - Interview
PSE	60-90 minutes	Semi-structured interview

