Exploratory analyses will extend the primary linear mixed-effects model by adding baseline variables (age, sex, educational level, baseline HAM-D6, duration of untreated depression, age at first episode, psychiatric/physical comorbidity, prior treatment history and DART score). If deemed feasible, non-linear dynamics as the interaction with treatment arm or an estimation using splines will be included. Relevant effects will be reported as regression coefficients or odds ratios with 95 % CIs and visualised in stratified plots where relevant.

All model assumptions are checked visually and sensitivity analyses, using bootstrap to estimate standard errors, are conducted in case of any violations.

All secondary outcomes will be analysed regardless of the significance of the primary outcome.

The statistical analyses will be performed by a statistician at the Department of Psychiatric Research, Aalborg University Hospital, Psychiatry, using Stata 19.

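### Exclusion criterion 8 is worded as an entry requirement, so as written it bars patients without recently started treatment and admits only those with it

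*Protocol*

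**What the plan says.** The protocol lists eight inclusion and eight exclusion criteria. The last exclusion criterion is "No current medical or psychotherapy treatment initiated within the last 4 weeks prior to screening".

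Three other places bear on what this item should do:

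- **Study population** describes patients with unipolar depression "in which there is clinical uncertainty as to which of the initial treatments (medication or psychotherapy) would be most beneficial".
- **Inclusion criteria, item 3** requires "Clinical uncertainty regarding which of the treatments, medication or psychotherapy, would be the better choice in the case concerned".
- **Study intervention**, describing the ALGO arm, says "Figure 2 illustrates the baseline measurement of HAM-D6, followed by initial treatment".

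On timing, Table of Measurements places both the eligibility check and randomisation at the screening visit, and says that "the first treatment visit (baseline visit) will be scheduled within 14 days of the screening". Study design gives the durations as "12 weeks of treatment and up to 2 weeks between screening and baseline".

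**The concern.** An exclusion list works by one rule: if the statement is true of the patient, the patient is out. Items 1 to 7 follow it (substance misuse, language difficulty, dementia, interfering medical conditions, pregnancy, risk of non-adherence, suicidality). Item 8 is phrased the other way round, as something a patient would have to satisfy to get in. Left in the exclusion list, it reverses its own effect.

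The item helps decide who is randomised, and it is the only criterion on current treatment. Several people have to apply it: GPs in multiple practices identify patients, and Recruitment of study participants allows the screening visit to be delegated to a research assistant. If all of them read it in the probable intended sense, the trial enrols people who formally meet an exclusion criterion. If any of them follow it literally, the trial enrols people whose treatment has already begun, which could weaken the contrast between starting pathways that the trial is meant to compare.

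**Working it through.** No figure in the protocol needs reproducing here. The check is to apply item 8 to each type of patient, first as placed and then as a requirement.

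| Patient at screening | Is the item 8 statement true? | As an exclusion (as placed) | As a requirement |
|---|---|---|---|
| (a) No current treatment | Yes | Excluded | Passes |
| (b) Current treatment, started more than 4 weeks ago | Yes, nothing was started in the window | Excluded | Passes |
| (c) Current treatment, started within the last 4 weeks | No | Passes | Excluded |

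The two readings give opposite answers in every row.

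**Against the rest of the protocol.** The literal reading admits only row (c). Study population treats the choice of first treatment as still open, which does not fit a trial made up solely of patients who have just started one. Two other passages point the same way but more weakly: the Figure 2 description covers the ALGO arm only, and inclusion item 3 requires uncertainty about the better treatment without saying that the patient is untreated.

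**Does anything else correct it?** Eligibility items dealing with current treatment: 0 of 8 inclusion + 1 of 8 exclusion = 1 of 16. Inclusion item 7 concerns willingness to be treated, not treatment already under way. Demographic data lists "Duration of untreated depression" and the exploratory models in Statistics include "duration of untreated depression, age at first episode", but these are a descriptor and a covariate, not entry rules.

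**Timing under the literal reading only.** Inputs: 4 weeks before screening = 28 days (item 8); at most 2 weeks from screening to baseline = 14 days (Study design, Table of Measurements); 12 weeks of treatment = 84 days (Study design).

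- Longest time from treatment start to baseline HAM-D6: 28 + 14 = 42 days.
- As a share of the treatment period: 42 / 84 = 0.50.
- Table of Measurements also allows visits 3 days either way. If that window extends the 14-day limit, which the document does not say, the figures are 28 + 17 = 45 days and 45 / 84 = 0.54.

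These are limits on what the literal rule would permit, not expected effects.

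**The case against.** The strongest reply is that this is a familiar drafting slip with little practical risk. Any reader who knows the trial will see that a requirement was left in the wrong list, and Study population and inclusion item 3 both steer away from the literal sense. Even if the rule were followed literally, randomisation would be expected to spread prior treatment over the three arms, so the comparison would not be biased by that alone. This stands, and it limits the weight of the point.

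The 42-day figure can also be challenged. It applies only to a reading that staff are unlikely to follow. Under the probable intended reading, row (b) patients pass, and their treatment could have begun at any time more than 28 days before screening, so exposure before baseline could be longer still. This stands too: the figure does not measure the harm done by the wording, and the point does not depend on it.

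Finally, whether row (b) patients should enter is a separate question of scope that does not follow from the inversion. That is fair. It is raised here only because whoever rewords the item will meet it.

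What the reply does not remove is the defect. The sentence is complete and numbered, no other criterion repairs it, and eligibility belongs in the protocol, so an analysis plan would not be expected to put it right. Inferring the intended sense still leaves enrolled participants meeting an exclusion criterion as written.

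**Conclusion.** The concern holds. Item 8 is wrong as written: one of eight exclusion items is inverted, and it is the only one of 16 eligibility items on current treatment. It should be fixed, because it is a rule applied at screening and randomisation that gives the opposite of what Study population describes.

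Confidence is high for the wording defect and does not extend to any consequence for the results. The sample size is unaffected, no bias between arms is claimed, and the protocol gives nothing from which an effect on HAM-D6 change could be estimated. Any dilution of the contrast between pathways depends on staff following the literal rule and on the earlier treatment affecting later change; the document is silent on both. It also does not show whether the screening form or eCRF repeats the wording.

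**What to change.** Reconcile item 8 with Study population, Study intervention and the Inclusion criteria. Either rephrase it as a condition whose presence excludes, in line with items 1 to 7, or move the sentence to the inclusion list. Check that the screening form and eCRF item carry the same sense.

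As a secondary clarification, the sponsor should state whether patients on treatment that started more than 4 weeks before screening may enter. Which rule applies is the sponsor's decision; the text should make it explicit.

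The cost is one line of protocol text, one eCRF check and one sponsor decision. If screening has begun, the criterion 8 entries already made should be checked against the intended sense.
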